7.10. Clinical Findings

The following analyses will be conducted in the AT population. These analyses except listings will also be conducted by country. The listings will be based on the enrolled population.

- The summary statistics will be presented for the number of days from the start of Cycle 1 treatment to the first onset of clinical findings of grade 1 or higher, the number of days to the worst grade, the number of days from the first onset to the outcome of recovery, and the number of days from clinical findings of grade 3 or higher to recovery to grade 2 or less in each treatment arm.
Clinical findings to be evaluated are stomatitis, anorexia, diarrhea, peripheral sensory neuropathy, nausea, and fatigue.
- A list will be created for the time of onset of the clinical findings to be analyzed in each subject, the time of worst grade, the time of grade 3 or higher, and the time required for recovery in each treatment arm.

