- (6) Skin eruption: Skin eruption should be managed by appropriate measures such as dose reduction or dose interruption.
- (7) Platelet decrease: Appropriate measures, such as dose change (reduction) or dose interruption, should be taken.
- (8) Peripheral sensory neuropathy: Paresthesia or dysesthesia of hands, feet or area surrounding the mouth and lips (peripheral neuropathy) occurs in almost all patients from immediately after the administration of L-OHP. Carefully observe the patient's state because a constricted feeling of the larynx and pharynx (dysesthesia of the larynx and pharynx) may appear, and take appropriate measures such as dose reduction/interruption if such abnormalities occur.
- (9) Hypersensitivity: Appropriate measures, such as antihistamic agent or steroid, should be taken.
- (10) Renal disorder: Before and after treatment with CDDP, adequate hydration and coadministration of diuretics to maintain sufficient urinary volume shall be performed in order to prevent renal disorder. When renal insufficiency occurs, careful fluid management, electrolyte replacement, and if required, renal dialysis shall be performed to restore urinary volume.

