- Every 1 week starting on Day 1 of each treatment cycle if the next treatment cycle is delayed (the data may be collected within 7 days before the scheduled date). Examination is mandatory on Day 1 or the day before starting the study treatment specified in this protocol.
- End of treatment assessments must be completed within 14 days from the date of last dose of study drug.
- These data may be collected 30 days after last dose of study drug or until the start of new anti-tumor therapy, whichever comes first. In cases an AE/SAE related to study drug is not resolving, the safety follow-up period will be extended.
- Obtain survival status (alive/ dead) at scheduled 12-week time intervals from randomization until death, and at the cutoff date for second interim analysis and primary evaluation (the data may be collected within 2 weeks before or after the scheduled date).

Table 11.2-2 A Study Schedule Arm B (S-1/CDDP)

Procedure	Pretreatment Period				Study Treatment Period				Post-treatment Follow-up Period			
	within 28 days prior to randomization	within 21 days prior to randomization	within 14 days prior to randomization	within 7 days prior to Day 1 of the first treatment cycle ^c	Arm B				End of Treatment ^m (+14 days)	Safety Follow-up ⁿ 30 days after last dose of study treatment (+14 days)	Tumor Follow-up Every 6 weeks (+/- 1 week)	Survival Follow-up Every 12 weeks (+/- 2 weeks)
					Day 1	Day 8 ⁱ (Day 6 to 15) (Japan)	Day 15 ^j (Day 8 to 22)	Before Initiation of next treatment cycle ^{k,1} Day36 (Day 29 to 43)				
S-1 treatment					X ^f (Day 1 - 21)							
CDDP treatment (Korea)					X ^f							
CDDP treatment (Japan)						X ^g						
Signed ICF	X											
Patient Background	X											
Height			X									
Pregnancy Test ^a			X									
Weight			X	X				→ ^h	X	X		
ECOG PS			X	X				→ ^h	X	X		
Blood Pressure			X	X				→ ^h		→ ^h		
Body Temperature			X	X				→ ^h		→ ^h		
ECG			X					→ ^h		→ ^h		
Physical Examination			X	X		X ⁱ	X	X	X	X		
Hematology			X	X		X ⁱ	X	X	X	X		
Serum Chemistry ^b			X	X		X ⁱ	X	X	X	X		
Urinalysis ^b			X	X		X ⁱ	X	X	X	X		
Tumor Markers ^c			X	→	→	→	→	→	→	→	X	
Tumor Measurements ^c		X		→	→	→	→	→	→	→	X	
Concomitant Medications ^d		X		→	→	→	→	→	→	X		
AE/SAE Assessment ^d		X		→	→	→	→	→	→	X		
Post Treatment												X
Survival Status					→	→	→	→	→	→	→	X ^o

- a. If the patient is female and of childbearing potential, a pregnancy test (serum or urine) must be done and the results must be negative at baseline.

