- (1) Related: The AE is related if it follows a reasonable temporal sequence from administration of study medication.
- (2) Not related: The AE is not related when there is no reasonable possibility that the study medication caused the event. For the purposes of safety reporting, “no

reasonable possibility” means there is no evidence to suggest a causal relationship between the drug and the adverse event and one or more of the following conditions are true:

- Disease Under Study
- Medical Condition(s)
- Previous or Concomitant Medication
- Protocol-related Procedure
- Other

Outcome:

- Resolved without sequelae
- Resolved with sequelae
- Resolving (Should be used only in the reporting SAE)
- Unresolved
- Death
- Unknown

Any ongoing AEs should be followed until the earliest occurrence of one of the following:

- AE has resolved
- Although the AE has not yet resolved, the Investigator considers that the AE is stable or no further improvement is expected. An AE cannot be considered stabilized while the patient is on study medication. Ongoing AEs must be assessed for stabilization 30 days post after the last dose of study medication
- The start of new anti-tumor therapy
- Patient meets one of the survival follow-up discontinuation criteria
- Safety follow-up becomes impossible due to changing hospital or other reasons
- Patient wishes to discontinue the safety follow up (including withdrawal of consent)

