5.2.1.2 Handling of Missing Data and Abnormal Values

No imputation of missing data will be performed. All data accepted at each time point will be used for the analysis. The proportion of subjects with adverse events and other proportions will be calculated using the analysis population as the denominator.

All data measured will be used for the analysis unless the cause of abnormalities is obvious, such as laboratory abnormalities caused by hemolysis during blood collection. If there are abnormalities to be

excluded from the analysis, these values will be identified, and the reason for exclusion will be justified.

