5.2.3. Statistical Methods

5.2.3.1 Summary Statistics for Continuous Data

Summary statistics for continuous data, if indicated, include the sample size, minimum, maximum, median, first quartile, third quartile, mean, and standard deviation.

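### SAP 7.10 summarises days to recovery with plain statistics, so unrecovered subjects contribute no value and durations read short, more so the slower a finding resolves

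*SAP*

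**What the plan says.** SAP 7.10 (AT population, by arm and also by country) plans summary statistics for two recovery intervals. The first is "the number of days from the first onset to the outcome of recovery". The second, which concerns severe findings only, is "the number of days from clinical findings of grade 3 or higher to recovery to grade 2 or less in each treatment arm". The scope is stated: "Clinical findings to be evaluated are stomatitis, anorexia, diarrhea, peripheral sensory neuropathy, nausea, and fatigue". SAP 5.2.3.1 says that summary statistics "include the sample size, minimum, maximum, median, first quartile, third quartile, mean, and standard deviation". SAP 5.2.1.2 adds: "No imputation of missing data will be performed". Section 7.10 also plans a by-subject list that includes the time required for recovery. Protocol 16.3.3.3 (4) had planned only a list.

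Three places in the protocol govern how long an adverse event is followed:

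- **Section 13.1.2** ends safety follow-up 30 days after the last dose, at new anti-tumor therapy, or for other listed reasons. It has no exception for an unresolved event, although related events arising later must still be reported.
- **Section 15.1.1** says: "Any ongoing AEs should be followed until the earliest occurrence of one of the following". The list includes resolution, a judgement that the event has stabilised or will not improve further, new anti-tumor therapy, transfer and withdrawal. Stabilisation must be assessed 30 days after the last dose.
- **The safety follow-up footnotes to Tables 11.2-1 and 11.2-2**, worded alike for the two arms, say: "In cases an AE/SAE related to study drug is not resolving, the safety follow-up period will be extended".

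**The concern.** Time to recovery is a time-to-event quantity, and some subjects will be unrecovered when observation of the event ends. Under plain statistics with no imputation they have no value to enter. The retained sample is selected for fast recovery, and the selection is stronger the slower the true recovery.

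Safety is a named secondary endpoint, and Arm A is the only arm given L-OHP as study treatment. Protocol 10.2.3 (8) says that paresthesia or dysesthesia "occurs in almost all patients from immediately after the administration of L-OHP". If such findings resolve slowly, a reader of the 7.10 table would see a short median and take the toxicity to be brief.

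The SAP already has the tools. Section 7.9 defines who counts as not recovered for laboratory values, and section 7.1.1.5 estimates a survival curve for duration of response. Section 7.10 has neither device.

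**Working it through.** The documents state no recovery time, so there is no planned figure to reproduce.

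**Step 1: who contributes a value.** The interval ends at the recovery outcome (SAP 7.10). No end date is supplied for a subject without one (SAP 5.2.1.2), and none of the listed statistics accommodates a censored value (SAP 5.2.3.1). Only recovered subjects contribute. The SAP does not say this outright; it follows from the three sections together.

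**Step 2: illustration of the effect.** All inputs are assumptions. Recovery is exponential with true median m, so λ = ln 2 / m. Follow-up from onset is uniform from a = 1 to b = 10 months and independent of recovery.

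- Share seen to recover: R = 1 − (e^(−λa) − e^(−λb)) / (λ(b − a)).
- Recovered-only median t (with t above a) solves 1 − [(b − t)e^(−λt) + (e^(−λa) − e^(−λt))/λ] / (b − a) = R/2.

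For m = 6: λ = 0.1155, R = 1 − (0.8909 − 0.3150)/(0.1155 × 9) = 0.446, and t = 2.28.

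| True median (months) | Seen to recover | Tabulated median (months) |
|---|---|---|
| 3 | 67% | 1.8 |
| 6 | 45% | 2.3 |
| 12 | 26% | 2.6 |

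A fourfold range of true medians is tabulated as 1.8 to 2.6.

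**Step 3: other follow-up windows.** Simulation with 200,000 subjects per setting, in days:

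| Follow-up from onset | Tabulated, true median 60 | Tabulated, true median 365 | Ratio of tabulated medians |
|---|---|---|---|
| 30–120 | 28 | 36 | 1.3 |
| 30–240 | 40 | 64 | 1.6 |
| 60–365 | 49 | 95 | 1.9 |

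The true ratio is 365/60 = 6.1. The direction is the same in every window; the size depends on the window.

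**Step 4: subjects who never recover.** Let a fraction p never recover and the rest have a median of 60 days, with follow-up of 30–240 days. The recovered-only median is 40 days whatever p is, because these subjects never enter. The true overall median is 60 × log2[(1 − p)/(0.5 − p)]: 85 days at p = 0.2, 155 days at p = 0.4, and not reached at p = 0.6.

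**Step 5: which estimator.** In these exercises Kaplan-Meier returns the true median wherever follow-up is long enough to reach it, but only because follow-up was made independent of recovery. Protocol 15.1.1 lets follow-up end because no further improvement is expected. Censoring those subjects treats them as likely to recover as the subjects still being followed, so recovery would still look too fast. Death also rules out later recovery.

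**The case against.** The best defence is that the table hides little. Sample size is among the statistics, and the same bullet summarises days to first onset. Subtracting one N from the other gives the number without a recovery time, by finding and arm. By-subject recovery times are listed, and event outcome and course are listed too (Protocol 16.3.3.3, SAP 7.2.1). SAP section 9 calls its analyses representative and refers to a separate output plan. This stands in part. A careful reader can tell that subjects are missing, but the subtraction works only for the any-grade interval, and no count corrects the median. An output plan that is not available cannot be credited with a censoring rule.

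Several stronger readings are tempting, and the documents do not support them:

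- **Follow-up of an ongoing event simply stops soon after the last dose.** Protocol 15.1.1 requires a stability check at 30 days, not a stop, and the footnotes extend follow-up for unresolved related events. The tension is with the flat 30-day stop in 13.1.2.
- **The arms are followed differently.** The footnotes match, and 15.1.1 covers both arms.
- **A planned between-arm comparison is biased.** Section 7.10 plans no test and no estimated difference.
- **The protocol shows that neuropathy lasts.** Section 10.2.3 (8) describes frequency and onset, not duration.
- **The recovery summaries in SAP 7.9 have the same gap.** They measure recovery within the onset cycle and already define who is not recovered.

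**Conclusion.** The point holds for the two recovery intervals in SAP 7.10. As written, they describe recovered subjects only and run short, and the shortfall grows with the true duration. Extended follow-up lessens this but does not remove it. Under 15.1.1, new therapy or judged stability still ends observation, and subjects who never recover still have no value.

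The direction rests on one inference, that subjects without a recovery outcome are left out, and no other workable reading of the text is apparent. The size cannot be derived from the documents: every recovery time and follow-up window above is assumed. That neuropathy is among the slower findings is also an assumption. The affected output is a descriptive secondary safety table. It deserves correction because following the plan gives a misleading median, but it touches neither overall survival nor any tested endpoint.

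**What to change.** **SAP 7.10, counts.** For each finding and arm, report the number with onset, the number recovered, and the number unresolved at last assessment, including those whose follow-up ended as stable or with no further improvement expected. Do the same for subjects who reached grade 3 or higher.

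**SAP 7.10, estimate.** Replace the recovered-only statistics for both intervals with the cumulative incidence of recovery in all subjects with the finding (or with grade 3 or higher, for the second interval):

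- death is a competing event;
- subjects closed as stable or without prospect of improvement stay in the denominator as not recovered;
- other unresolved subjects, including those who start new therapy, are censored at last assessment, and the SAP states that this censoring is assumed non-informative.

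**Protocol.** Reconcile the 30-day stop in 13.1.2 with 15.1.1 and the safety follow-up footnotes to Tables 11.2-1 and 11.2-2, so that the last assessment date has one meaning.

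**Cost.** A SAP revision and a modest amount of programming. No new data are needed: Protocol 15.1.1 already requires onset date, resolution date and outcome, and Protocol 19.1 lists the reason for ending follow-up among the items entered in the case report form. The drawback is that some medians may be reported as not reached.

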7.11. Tumor Markers

The following analyses will be conducted in the AT population. These analyses except listings will also be conducted by country. The listings will be based on the enrolled population.

- The change in tumor markers over time will be graphed in each treatment arm.

